#### Potential Benefits:

Long-duration (vs short-duration opioids) may decrease the need for additional opioids in the immediate postoperative period, decrease possible side effects of opioids, improve immediate postoperative pain relief and may decrease the occurrence of chronic postoperative pain.

Successful completion of this research is expected to result in improved pediatric surgical care, enhanced patient recovery and pain management requiring less post-operative opioids. Anesthetic risks associated with long-duration and short-duration opioids are similar, and, in light of improved pain relief demonstrated in adult studies, there is sufficient clinical justification to conduct this research in children.

### **Data Analysis & Statistical Considerations**

Descriptive statistics for each treatment group will be computed for patient demographic and characteristic variables. Since our randomization scheme will have balanced the age effect between treatment groups, we anticipate the demographic and patient characteristic variables will be balanced across groups. For the continuous outcome measures (primary and most of secondary outcomes), we will conduct two-sample t-test to test the outcome difference (e.g., total OME difference) between treatment groups. For categorical outcomes (e.g., PACU side effects and adverse events), chi-square or Fisher exact tests will be applied as appropriate. Considering this is a pilot study for dose finding, we will relax the significance threshold to 0.1 for the interim analysis. Using the primary outcome, total OME/kg as an example, a two-sample t-test will be performed for comparing total OME difference between 20 methadone (0.1mg/kg) treated patients to 10 controls based on significance threshold of 0.10. If methadone showed significant effect on the outcome measure, the higher dose arm (0.15 mg/kg age ideal body weight) will be pursued. In the final analysis, similarly, two-sample test

will be used to test the total OME difference between methadone and control groups for both dose levels. To correct for multiple testing, the significance threshold in the final analysis will be set at 0.025. If there are covariates showing significant difference between treatment groups, we will perform multivariable linear regression analysis to test the treatment effect after adjusting for one selected covariate and examine if the treatment effect remains the same as that found in the two-sample t-test. The reason to restrict to one covariate in the model was to avoid model overfitting considering there will be only 20 samples per group. Similar analysis strategy will be applied to other outcome measures.

Power calculation: Two-sample t-test with an assumption of equal variance between groups was used to estimate statistical power. For the interim analysis based on 20 methadone 0.1mg/kg cases and 10 controls, assuming standard deviation (SD) total OME as 0.3, our proposed sample size will have 80% power to detect 0.3 OME difference at the significance level (alpha) of 0.1. Assuming we can move forward to the higher dose cohort, the final analysis will include two tests to compare 20 cases vs. 20 controls for each methadone dose level. In this scenario, assuming the same OME variability of SD=0.3 and the reduced alpha level to 0.025, our proposed sample size (N=20/group) can detect the 0.31 OME difference between methadone and control groups with 82% power, a similar effect size as the interim analysis. The detectable mean difference will increase if the OME variability (SD) increases.

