#### **Study Interventions**

Study Intervention and Randomization: Subjects in each cohort will be randomized 2:1 methadone to short acting opioid using randomization tables generated by The Biostatistics Group within the Department of Anesthesia. Each subject is assigned the next number. To consider children in different age may have different pain tolerance, we will balance the treatment groups by age. That is, we will generate a set of blocked randomization numbers for three age groups, 3-6, 7-12, and 13-17 years old. Anesthesia providers receive a sealed envelope or email with Group (drug) assignment, group-specific instructions, and are advised on study procedures. To ensure full double-blinding, subjects, investigators, and study team members evaluating patients will be blinded to drug treatment. The rationale for 2:1 randomization is to achieve the same sample size for each group since we anticipate 2 methadone cohorts, thus final groups (methadone 0.1 mg/kg, methadone 0.15 mg/kg, controls) would each have 20 subjects.

As clarified above, the use of a short duration opioid in this specific study population (tonsillectomy 3-18 year olds) is a standard of care procedure. Methadone is standard of care in pediatric cardiac surgery, pediatric spine surgery and precuts excavatum surgery (3-18 year olds). Not counting the randomization, the dosing and administration of all 3 of these drugs (methadone, fentanyl, hydromorphone) are in line with standard of care practices for pediatric population of between 3 and less than 18 years and are routinely used both in and out of the operating room environment.

Regarding the clinical study of an investigational drug that would be IND exempt, the following ARE true for this study (see below):

- The investigation of a drug that is lawfully marketed in the US and the following 5 criteria are met:

the study is not designed to support approval of a new indication or change in labelling: No new indications sought

the study does not intend to support significant change in advertising of the product: No new advertising sought

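### Randomisation is blocked by age group but the primary test is an unadjusted t-test: conservative if age is prognostic, with a power change from adjustment of about −1 to +6 points for an assumed age R² of 0 to 0.2

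*Combined protocol and SAP*

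**What the plan says.** Study Interventions gives the reason for stratifying: "To consider children in different age may have different pain tolerance, we will balance the treatment groups by age". It then gives the method: "we will generate a set of blocked randomization numbers for three age groups, 3-6, 7-12, and 13-17 years old". Allocation is 2:1 within each cohort, and block size is not stated.

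Data Analysis & Statistical Considerations relies on that balance ("Since our randomization scheme will have balanced the age effect between treatment groups") and then sets an unadjusted comparison: "For the continuous outcome measures (primary and most of secondary outcomes), we will conduct two-sample t-test to test the outcome difference". The interim test is the same: "Using the primary outcome, total OME/kg as an example, a two-sample t-test will be performed", at a threshold of 0.10. The final tests use 0.025.

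Adjustment is conditional: "If there are covariates showing significant difference between treatment groups, we will perform multivariable linear regression analysis". One selected covariate may enter, and the model serves to see whether the t-test result is unchanged. The stated reason for the limit is "The reason to restrict to one covariate in the model was to avoid model overfitting".

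The power calculation in the same section assumes an equal-variance t-test, and "the final analysis will include two tests to compare 20 cases vs. 20 controls for each methadone dose level".

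**The concern.** The plan treats age as possibly prognostic when it randomises and leaves age out when it analyses. Balance by design is not a reason to omit the factor. Blocking makes the arms alike in age, so age contributes little to the sampling variation of the mean difference. The pooled t-test does not use this: between-age variation stays in its residual variance. If age matters, the reported standard error exceeds the true spread of the estimate, p-values are too large, and the test rejects less often than its nominal level.

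The conditional regression does not repair this. It is triggered by imbalance, and age is the factor least likely to be imbalanced.

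At stake is the precision reported from comparisons with 10 to 20 children per group. Nothing is argued here from the escalation decision. Design & Procedures escalates when there is no difference in PACU opioid use, while the analysis section escalates on a significant effect. Those passages must be reconciled before anyone can say which decision a more powerful interim test would favour.

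**Working it through.** **Inputs from the documents** (Power calculation): SD 0.3. Interim: 20 vs 10, difference 0.30, alpha 0.10. Final: 20 vs 20, difference 0.31, alpha 0.025.

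**Assumed, because the documents give no value:** the share of outcome variance explained by age, R² = 0 to 0.2 (small values are plausible, since the outcome is per kg); block size 3 or 6; age mix 40/40/20 over the three strata.

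**Step 1. Reproduce the plan's power.** SE = SD × √(1/n₁ + 1/n₂); power from the two-sided noncentral t.
- Interim: SE = 0.3 × √(1/20 + 1/10) = 0.116; noncentrality 0.30/0.116 = 2.58; 28 df; power 80.9% (plan: 80%).
- Final: SE = 0.3 × √(1/20 + 1/20) = 0.0949; noncentrality 0.31/0.0949 = 3.27; 38 df; power 82.0% (plan: 82%).

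**Step 2. Limiting case by hand.** With perfect age balance the true SD of the estimate is SE × √(1 − R²), while the t-test still reports about SE. At R² = 0.2, √0.8 = 0.894.
- Interim: true SD 0.116 × 0.894 = 0.104. The critical value 1.701 acts like 1.701/0.894 = 1.90, so size is about 0.068 instead of 0.10.
- Final: true SD 0.0949 × 0.894 = 0.085. The critical value 2.334 acts like 2.334/0.894 = 2.61, so size is about 0.013 instead of 0.025.

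**Step 3. Simulate the design.** There were 40,000 replicates per cell. Each 30-child cohort was allocated 2:1 in permuted blocks within age stratum. The final test compares the second methadone cohort with controls pooled from both cohorts. Age acts stepwise by stratum or linearly in years, and errors are normal with equal variance. Ranges cover both block sizes and both shapes. The power change is from the t-test to the model with age stratum.

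| Test | R² | Power change (points) | True size of t-test | t-test SE too wide by |
|---|---|---|---|---|
| Interim (nominal 0.10) | 0 | −0.3 to −0.6 | nominal | none |
| | 0.05 | +0.4 to +0.8 | not listed | about 1% |
| | 0.1 | +1.7 to +2.1 | 0.084–0.087 | 3–5% |
| | 0.2 | +4.0 to +4.6 | 0.069–0.075 | 8–10% |
| Final (nominal 0.025) | 0 | −0.7 to −0.8 | nominal | none |
| | 0.05 | +0.7 to +1.0 | not listed | about 1% |
| | 0.1 | +2.0 to +2.6 | 0.019–0.021 | 3–4% |
| | 0.2 | +5.0 to +5.9 | 0.015–0.017 | 7–8% |

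At R² = 0.2, power goes from 82.0–83.2% to 86.1–87.8% (interim) and from 83.4–83.7% to 88.4–89.6% (final). The adjusted model holds its size: 0.099–0.102 interim and 0.024–0.026 final. Age in years as one term gives powers within 1.5 points of these.

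**Step 4. Locate the cause.** At R² = 0.2 the true spread of the estimate hardly changes with adjustment: interim 0.105–0.108 unadjusted against 0.104–0.106 adjusted, final 0.088 against 0.086–0.087. The t-test's mean standard error is 0.116 and 0.0945. The gain therefore comes from a correct standard error, not from a better estimate.

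**Step 5. Test the fallback.** The significant-difference rule would select age in at most 0.3% of trials at p<0.05 and under 1% at p<0.10. The plan gives no threshold.

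**Step 6. Express as sample size.** In the final test, 20 per group with adjustment matches the t-test at about 20.5 (R² = 0.05), 21–21.5 (R² = 0.1) or 22.5–23 (R² = 0.2) per group.

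An independent calculation with near-exact age balance gave +5.8 points (final) and +6.7 (interim) at R² = 0.2. Under different balance assumptions, t-test sizes at that R² run from about 0.066 to 0.075 (interim) and 0.011 to 0.017 (final). The tenths in the table should not be over-read.

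**The case against.** **Nothing promised fails.** Under the plan's assumptions the t-test does not inflate type I error, and the stated power is met. This stands: the point is about efficiency and correct uncertainty in a pilot, and it is sized accordingly.

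**The gain rests on an assumed R².** This also stands. At R² = 0.05 the gain is at most 1 point, about half a child per group, and at R² = 0 there is a small loss. The documents do not favour 0.2 over 0.

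**Unequal variance.** If methadone also halves the residual SD, ordinary least squares at the 20 vs 10 interim has size about 0.19–0.20 against 0.10 at R² = 0.2, compared with about 0.11 for the pooled t-test. This reproduces, so the claims of conservatism and near-zero cost at the interim depend on equal variance. It does not defend the planned test: in that setting the pooled t-test itself has size about 0.18 at R² = 0, and the plan's own calculation assumes equal variance. A robust standard error brings the adjusted test back to about 0.12. The 20 vs 20 final test is little affected (0.025–0.029).

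**Overfitting and planned outputs.** The one-covariate limit does not exclude age: age in years uses one parameter and stratum uses two. The plan mentions no confidence intervals, but the same standard error produces its p-values.

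**Conclusion.** The concern holds. The primary analysis does not use the age groups that the randomisation was built on, and the conditional regression will almost never bring age in. If age is prognostic, the t-test is conservative. Over an assumed R² of 0 to 0.2, adjusting for age changes power by about −1 to +6 points. At R² = 0.2 it corrects a standard error that is 7–10% too wide. These figures assume normal errors, equal variance, and controls pooled across cohorts as the power calculation counts them. The effect is small to moderate. The change is worth making because the plan itself regards age as relevant and the cost is close to nil.

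**What to change.** Pre-specify as the primary analysis, at interim and final, a linear model of the outcome on treatment plus randomisation age stratum (3–6, 7–12, 13–17 years). Test treatment at the thresholds already stated (0.10 and 0.025), and report the adjusted mean difference with a 90% (interim) or 97.5% (final) confidence interval. If the one-covariate limit is meant as one parameter, enter age in years as a single term. The SAP should name one of these before any unblinding, and say whether the imbalance-triggered regression may add a covariate beyond age. Keep the unadjusted t-test as a supporting analysis. At the interim, a robust standard error is a sensible sensitivity check for unequal spread.

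No cohort term is proposed for the pairwise final model. With one, only the 10 concurrent controls inform the contrast, and power falls to 62% at R² = 0 (72–73% at R² = 0.2). Whether controls may be pooled across cohorts is a separate question.

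Cost: SAP wording only. Age stratum is already known from randomisation. The model uses one or two degrees of freedom, and if age is not prognostic the loss is 0.3–0.8 point of power.

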#### **Design & Procedures**

Study Design: Single center, randomized, double blind, parallel-group dose escalation investigation. All patients will receive standard monitoring for anesthesia and postoperative care. Surgical and anesthesia care (except for intraoperative opioid management) are not altered for study purposes. Subjects are randomized 2:1 to either long-duration (methadone) or short-duration opioid (fentanyl, hydromorphone). The use of any short acting opioid (ie: fentanyl, hydromorphone or both) is considered the control group and total dose, timing of administration, frequency of administration, and dose per administration of either/both short acting opioids will be administered at the discretion of the anesthesiologist as per standard of care practice. Because methadone analgesia for pediatric tonsillectomy has not previously been studied, this pilot study will use escalating dose groups to determine the optimal dose for this procedure. In order to achieve this, our trial design will include two periods. In the first period, we will randomly assign 20 patients to methadone 0.1 mg/kg and 10 patients to typical shortduration opioid (controls). An interim analysis will be conducted to determine if we should escalate to the higher dose of methadone. Methadone dose escalation to 0.15mg/kg age ideal body weight will occur if there is no difference in non-methadone PACU opioid use and no increased adverse events. If proceeding to the second period, we will recruit 20 patients for 0.15 mg/kg methadone and 10 patients as controls. Sample size for this pilot investigation was based on prior studies.

Defining an optimal dose of methadone is a crucial aim of this study, which will allow for future investigations, but is not a primary or secondary outcome. The dose finding nature of this study requires interim assessments after each methadone dose cohort. After the first 20 methadone subjects at 0.1mg/kg age ideal body weight, there will be a planned partial analysis of PACU opioid use. Methadone dose escalation to 0.15mg/kg age ideal body weight will occur if there is no difference in non-methadone PACU opioid use and no increased adverse events. Sample size for this pilot investigation was based on prior studies.

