Pre-operative, Intra-operative, Post-operative Care: Anesthesia and surgical care are not altered for this study except for randomization to the study drug. Oral or IV midazolam for anxiolysis may be given at standard dosing. Anesthetic induction via inhaled sevoflurane or intravenous agents are to be given at the anesthesiologist's discretion.

Patients in the short-duration opioid group receive short-duration opioids (IV fentanyl and/or hydromorphone), given as needed throughout the intraoperative period, per usual practice at practitioner's discretion. Patients in the long-duration opioid group receive IV methadone HCl at 0.1mg/kg. These subjects receive methadone as their only intraoperative opioid, given as a single bolus at anesthetic induction. If needed, a second cohort will receive or 0.15mg/kg of age-based ideal body weight. Following extubation, patients may receive incremental doses of

0.1mg/kg up to a maximum of 0.5mg/kg of dexmedetomidine (dosed at age-based ideal body weight) for sedation if needed, contingent upon adequate ventilatory rate.

For analgesia in the Post-Anesthesia Care Unit (PACU), patients in both groups may receive typical short-duration opioids (fentanyl or hydromorphone) as per usual routine care. It is not necessary that patients receive the same opioid postoperatively as intraoperatively. Post-op opioids orders are written by the pediatric anesthesiologist and opioids are given by PACU nurses per standard practice, based on developmentally appropriate pain scales (FLACC, Wong-Baker Faces, VAS) and institutional practice.

Pain scores via developmentally appropriate and validated pediatric pain scales will be confirmed by a blinded research coordinator OR a blinded secondary pediatric PACU nurse and charted in the EMR prior to administration of opioid analgesics. Adverse events will be recorded by a research coordinator who is blinded to randomization allocation and include: Respiratory depression (respiratory rate <10/min), reintubation, decreased oxygen saturation <85% for 30 seconds, excessive sedation (Pasero Opioid-induced Sedation Scale (POSS) score 3>1 hour, 4>15 minutes), unexpected PICU admission, and vomiting in PACU.

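### The OME/kg t-tests have no rule for children who are over-sedated, given naloxone, reintubated or moved to the PICU, so an excess of such events under methadone can pass for opioid sparing

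*Combined protocol and SAP*

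**What the plan says.** Data Analysis & Statistical Considerations sets out the efficacy test: "Using the primary outcome, total OME/kg as an example, a two-sample t-test will be performed". For the interim look, "we will relax the significance threshold to 0.1 for the interim analysis", and the consequence is: "If methadone showed significant effect on the outcome measure, the higher dose arm (0.15 mg/kg age ideal body weight) will be pursued". Design & Procedures describes the interim variable more narrowly: "there will be a planned partial analysis of PACU opioid use".

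How the PACU part of the outcome arises is described in Design & Procedures: "opioids are given by PACU nurses per standard practice, based on developmentally appropriate pain scales", together with institutional practice. The same section lists the adverse events that a blinded coordinator records. They include slow breathing, reintubation, desaturation, excessive sedation on the POSS scale, "unexpected PICU admission, and vomiting in PACU". The statistics section analyses these by chi-square or Fisher tests. Naloxone is mentioned under Protections against Risk as a treatment, but it is not on the adverse event list.

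Aim 2 (Purpose of the Study) hypothesises lower opioid use and pain without more respiratory depression or excessive sedation. Escalation is addressed in three places. Design & Procedures requires no difference in PACU opioid use and no rise in adverse events. Protections against Risk requires that the first methadone dose group be free of adverse events. The statistics section requires a significant effect and names no safety condition.

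**The concern.** PACU opioid is given in response to pain scores. A child who is heavily sedated, breathing slowly, reintubated or taken to the PICU may receive little or none of it for reasons unrelated to good analgesia. The t-test cannot tell a child who needed no opioid from one who could not safely be given any. For a long-acting opioid this is a foreseeable route to a low value. If these events are more frequent under methadone, the estimated opioid reduction is too large and its p-value too small, both at the interim and in each final dose-versus-control comparison. A separate adverse event table leaves that estimate and p-value unchanged.

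**Working it through.** **1. Reproduce the plan's power.** The plan states, for 20 vs 10 at alpha 0.10: "assuming standard deviation (SD) total OME as 0.3, our proposed sample size will have 80% power to detect 0.3 OME difference". For 20 vs 20 at alpha 0.025 it states 82% power for a difference of 0.31. The noncentrality is difference / (SD × √(1/n₁ + 1/n₂)).
- Interim: 0.3 / (0.3 × √0.15) = 2.58 on 28 df. Two-sided t-test power is 80.9% (stated 80%).
- Final: 0.31 / (0.3 × √0.10) = 3.27 on 38 df. Power is 82.0% (stated 82%).

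The plan does not state sidedness, but only the two-sided t version matches both figures. The nominal rate of a false result in methadone's favour is therefore 0.10/2 = 5% at interim and 0.025/2 = 1.25% at the end. The sample size itself is not in question.

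**2. Artificial shift in the mean.** If k of 20 methadone children score zero and analgesia is equal, the methadone mean falls by (k/20) × mean OME. The documents give no control mean, so I take 0.3 to 0.6 as an assumption.
- k = 2: 0.03 to 0.06, at most 0.06/0.31 = 19% of the planned difference.
- k = 5: 0.075 to 0.15, at most 0.15/0.31 = 48%.

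**3. False-benefit rate.** There were 50,000 simulated trials per setting. Both arms came from one distribution (normal or gamma; mean 0.3, 0.45 or 0.6; SD 0.3). Then k methadone values were set to zero, with no control events. Normal draws were not floored at zero; the gamma draws, which cannot be negative, gave similar results. Ranges are across all settings.

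| Affected methadone children of 20 | Interim, 20 vs 10 (nominal 5%) | Final, 20 vs 20 (nominal 1.25%) |
|---|---|---|
| 0 | 5.0-5.9% | 1.2-1.3% |
| 1 | 6.2-7.5% | 1.7-2.2% |
| 2 | 8.2-10.2% | 2.4-3.7% |
| 4 | 12.8-18.9% | 4.7-10.2% |
| 5 | 16.0-25.5% | 6.7-16.1% |

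**4. Events in both arms.** With mean 0.6, SD 0.3 and a 10% event rate in each arm, the rates are 4.6% (interim) and about 1.3% (final), which is nominal. With 10% under methadone and 5% in controls they are 8.0% and 2.1%.

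**5. Would the separate adverse event test show the problem?** Take four events, all under methadone.
- Final, 20 vs 20: C(20,4)/C(40,4) = 4,845/91,390 = 0.053, doubled by symmetry to p = 0.106. At 5/20 p = 0.047, and at 6/20 p = 0.020, the first value below 0.025.
- Interim, 20 vs 10: (4,845 + 2,400 + 210)/27,405 gives p = 0.27. It first falls below 0.10 at 6/20 (p = 0.074).

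Four affected children would thus pass both Fisher tests while the final false-benefit rate is about 4 to 8 times nominal (4.7/1.25 = 3.8; 10.2/1.25 = 8.2).

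**6. Worst-rank scoring.** Event rates of 10%, 20% and 30% under methadone, with none in controls, were tried in a normal model (mean 0.6, SD 0.3) and a skewed model with zeros (mean 0.4, SD 0.35). A Wilcoxon test with affected children ranked worst kept false benefit at or below 0.4% at the final test and below 2% at interim.

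**The case against.** The strongest reply is that the plan already guards against mistaking harm for benefit. Adverse events are recorded blind and tested, Aim 2 couples less opioid with no excess of sedation or respiratory depression, and two of the three escalation statements carry a safety condition. This stands as far as it goes. A reader might infer from the statistics section alone that over-sedation could drive escalation to the higher dose. The documents do not support that: under Protections against Risk one adverse event in the first dose group would block escalation, and under Design & Procedures a significant opioid reduction would itself count against it. The interim percentages above are therefore not false-escalation rates.

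Second, the low score is an inference. No scoring rule is given, and the window for total OME is not defined in the supplied text. A child may have had opioid before becoming sedated, and a reintubated child might receive more later, which would count if the window runs beyond PACU. This also stands.

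Third, the size depends on an excess under methadone. Controls also receive opioids and possibly dexmedetomidine, Potential Benefits calls the anesthetic risks similar, and severe sleep apnea is excluded. A 30% event rate under methadone with none in controls (mean 0.6) gives 27-29% at the final test, but nothing in the documents supports that rate.

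What does not stand is that these safeguards repair the OME analysis. They govern escalation or sit in another table. The final tests, including the one at the higher dose, have no such condition. The sedation definition also has duration thresholds, so a child at POSS 3 for 50 minutes could have opioid withheld without counting as an event.

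**Conclusion.** The gap is real and should be closed; it is modest unless several children are affected. The plan does not say how these children enter the OME comparison, and an excess of harm under methadone would bias the estimate and p-value in its favour. One or two affected children of 20 take the final false-benefit rate to about 2-4%. Four or five take it to about 5-16%, where it becomes material. These figures rest on an assumed mean OME of 0.3 to 0.6, the plan's SD of 0.3, no control events and zero scores for affected children. The documents give no event rate and no control mean.

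A reader might conclude that the plan simply counts methadone harm as methadone benefit. That goes too far, because harm is measured, tested and part of the Aim 2 hypothesis. The defect is confined to the OME test itself.

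**What to change.** In Data Analysis & Statistical Considerations:

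1. State the time window and the opioids that make up total OME/kg.
2. Beside the interim and final t-tests, prespecify a sensitivity analysis. Children with reintubation, unexpected PICU admission, protocol-defined respiratory depression or excessive sedation, or naloxone receive the worst rank, and arms are compared by a Wilcoxon test.
3. Report it with a joint table of OME and adverse events by arm. Call an opioid reduction robust only if the sensitivity analysis points the same way.

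Separately, the escalation conditions in Design & Procedures, Protections against Risk and the statistics section contradict each other and must be reconciled. I take no view on which is right.

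The trigger should be objective events, not a judgement that opioid was withheld: anesthesia providers receive the assignment and anesthesiologists write the PACU orders, so a discretionary trigger could be applied with knowledge of the arm. The price is that children below the event thresholds whose opioid was withheld stay uncorrected.

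The sensitivity analysis should not become a second significance gate. In the mean 0.6, SD 0.3 model with a true reduction of 0.31, requiring both tests to be significant cuts final power from about 81% to about 60% at a 5% methadone event rate and 43% at 10%.

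The cost is a few lines of text, one rank test, and a naloxone field if the case report form lacks one. The benefit will look smaller if such events occur.

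### The flat 0.025 threshold for the two final dose comparisons is valid, but Holm's procedure would give more power within the same implied 5% family-wise limit

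*Combined protocol and SAP*

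**What the plan says.** The Data Analysis & Statistical Considerations section compares each methadone dose with control by a two-sample t-test and, as its correction for multiplicity, sets one threshold for both tests: "the significance threshold in the final analysis will be set at 0.025". The power calculation in that section confirms the structure: "the final analysis will include two tests to compare 20 cases vs. 20 controls for each methadone dose level". It works at "assuming the same OME variability of SD=0.3 and the reduced alpha level to 0.025" and concludes that the design "can detect the 0.31 OME difference between methadone and control groups with 82% power".

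Study Interventions shows that a single control group serves both tests: "final groups (methadone 0.1 mg/kg, methadone 0.15 mg/kg, controls) would each have 20 subjects".

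The plan describes no step-down, hierarchical or other joint procedure and gives no power for confirming both doses. It does not state a 5% family-wise level. That level is inferred from 2 × 0.025 = 0.05.

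**The concern.** The flat rule holds each dose to 0.025 whatever the other dose shows. Once one dose has passed at 0.025, the 5% family-wise limit no longer requires the second to meet so strict a threshold. Holm's step-down rule uses this: the second test is then made at 0.05. Its error control holds under any correlation between the tests, so sharing the control group does not affect its validity.

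What is at stake is power in a trial with 20 patients per group. A dose with a real effect and a p-value between 0.025 and 0.05 is not significant under the flat rule even when the other dose has clearly passed. This bears most on a dose with the smaller effect, in a study that wants to learn about both dose levels.

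**Working it through.** **Inputs from the documents.** Two final tests of 20 vs 20; SD 0.3; difference 0.31; 0.025 per test; one control group of 20; equal-variance t-test ("Two-sample t-test with an assumption of equal variance between groups was used to estimate statistical power"). Sidedness is not stated; two-sided is assumed because it reproduces the plan's figures.

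**Step 1: reproduce the plan's power.**
- Final: noncentrality = 0.31 / (0.3 × √(1/20 + 1/20)) = 3.27, with 38 degrees of freedom and critical t 2.334 at two-sided 0.025. Power is 82.0%; the plan states 82%. A one-sided t-test would give 89.0%, which does not match.
- Interim ("our proposed sample size will have 80% power to detect 0.3 OME difference at the significance level (alpha) of 0.1"): noncentrality = 0.3 / (0.3 × √(1/20 + 1/10)) = 2.58, with 28 degrees of freedom. Power is 80.9%; the plan states 80%.

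**Step 2: define the two rules.** Let p(1) ≤ p(2) be the ordered p-values.
- Flat: reject each dose with p < 0.025.
- Holm: reject the dose with p(1) if p(1) < 0.025; if so, also reject the other if p(2) < 0.05 (critical t 2.024).

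Holm therefore adds a rejection only when one p-value is below 0.025 and the other lies between 0.025 and 0.05. It removes none.

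**Step 3: power if the second cohort opens.** Simulated t-tests with a shared control group, SD 0.3, 20 per group (1,000,000 trials in the main run with both differences 0.31):

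| True differences | Quantity | Flat | Holm |
|---|---|---|---|
| 0.31 and 0.31 | each dose significant | 82.0% | 86.7% |
| 0.31 and 0.31 | both significant | 71.6% | 80.8% |
| 0.31 and 0.31 | at least one significant | 92.5% | 92.5% |
| 0.20 and 0.31 | weaker dose significant | 42% | 52% |

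Two checks tie the rows together. At least one = 82.05 + 82.05 − 71.6 = 92.5%. The joint gain, 80.8 − 71.6 = 9.2 points, is by symmetry twice the per-dose gain, 9.2 / 2 = 4.6 points. They are one gain counted in two ways, not two gains. A bivariate normal check with correlation 0.5, calibrated to 82% per test, gives 71.5% and 80.2% for both doses.

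**Step 4: error rates.**

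| Situation | Error | Flat | Holm |
|---|---|---|---|
| Neither dose works | at least one false rejection | 4.7% | 4.7% |
| One dose differs by 0.31, the other is null | false rejection of the null dose | 2.5% | 4.3% |
| One dose has a very large effect, the other is null | false rejection of the null dose | 2.5% | 5.0% |

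**Step 5: count the interim decision.** The figures in Step 3 assume escalation, as the plan's own 82% does. The documents give two statistical conditions for escalating. The Data Analysis section escalates if the 0.1 mg/kg dose shows a significant effect at 0.10. Design & Procedures escalates if PACU opioid use does not differ and adverse events are not increased. The second is read here as p ≥ 0.10, leaving out its safety condition, and both are applied to the same simulated outcome (20 methadone patients and the first 10 controls; both true differences 0.31):

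| Escalation condition | Chance of escalating | Escalate and confirm both: flat | Holm |
|---|---|---|---|
| Data Analysis section (p < 0.10) | 83% | 67% | 74% |
| Design & Procedures (p ≥ 0.10) | 17% | 4% | 7% |

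**Step 6: sensitivity.** With SD 0.4 (an assumption, not in the plan) and both differences 0.31, power for both doses is 38.6% flat and 50.0% with Holm.

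**The case against.** The strongest reply is that nothing is wrong. A 0.025 threshold for two tests is a valid correction and agrees with the power calculation, which reproduces. That stands: this is a choice between two valid methods.

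A reader might also infer that the trial loses about 10 points of power on its own objective. The documents do not support that. They power each comparison separately and nowhere require both doses to be confirmed, and Design & Procedures says that defining the optimal dose is neither a primary nor a secondary outcome. On the plan's own measure, per-dose power, the gain is just under 5 points, and the chance of at least one significant dose does not move.

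Nor do the documents say that a dose missing 0.025 would be declared ineffective. They attach no such consequence to the final test.

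It is also fair to say that Holm is not free. Steps 3 and 4 show a trade: extra power for the second dose is bought with a higher false-positive rate for a null dose when the other works, still within 5%. Simple 97.5% intervals will disagree with the test in exactly the cases where Holm adds a rejection, because an interval at that level excludes zero only when p < 0.025.

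Finally, the gain exists only if there is a second dose. Under Unblinding Procedures the study may resume at 0.1 mg/kg, and then there is no second dose comparison and Holm changes nothing.

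**Conclusion.** The point holds as a cheap improvement. The flat rule is sound, but at the family-wise level it implies, Holm rejects everything it rejects and sometimes more. That ordering does not depend on the assumed SD or effects; the size of the gain does.

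Given escalation, SD 0.3, shared controls, two-sided tests and true differences of 0.31, the gain is 82% to 87% per dose and 72% to 81% for both. For a weaker dose at 0.20 beside one at 0.31, it is 42% to 52%. Before escalation is known, the gain in confirming both is about 7 points under the Data Analysis condition and about 3 points under the Design & Procedures condition. Those two sections contradict each other and must be reconciled. That conflict matters more than this point, because it decides whether a second comparison takes place.

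**What to change.** In the Data Analysis & Statistical Considerations section, replace the fixed threshold with Holm's procedure at family-wise 0.05 over the two final dose-versus-control tests, stating the 5% level explicitly. Specify it before final unblinding.

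In the power calculation, keep the 82% and describe it as a lower bound on per-dose power for the stated assumptions; no change to the sample size is needed.

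Add one line saying that 97.5% confidence intervals will be reported and that a dose rejected at p between 0.025 and 0.05 will have an interval that includes zero. Record also that the chance of a false positive for one null dose can approach 5% when the other dose works.

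The cost is a few sentences and no extra patients. Separately, reconcile the escalation conditions in Design & Procedures and the Data Analysis section.
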